8.5 Treatment of Overdose

For purposes of this study, an overdose will be defined as any dose of any drug administered as part of the study exceeding the dose prescribed by the protocol. It is up to the investigator or the reporting physician to decide whether a dose is to be considered an overdose, in consultation with the Sponsor.

Sponsor does not recommend specific treatment for an overdose.

8.6 Pharmacokinetics

08CYXG

The decision as to which plasma and/or urine samples collected will be measured for evaluation of PK/pharmacodynamics will be collaboratively determined by the Sponsor (eg, samples at lower doses may not be measured if samples at higher doses reveal undetectable

drug concentrations). If indicated, these samples may also be measured and/or pooled for assay in an exploratory manner for metabolites and/or additional pharmacodynamic markers.

8.6.1 Blood Collection for Plasma MK-8527 and PBMC MK-8527-TP

Sample collection, storage, and shipment instructions for plasma and PBMC samples will be provided in the operations/laboratory manual.

8.7 Pharmacodynamics

Sample collection, storage, and shipment instructions for pharmacodynamic samples will be in the operations/laboratory manual.

8.8 Biomarkers

Collection of samples for other biomarker research is also part of this study. The following samples for biomarker research are required and will be collected from all participants as specified in the SoA:

Blood for genetic analysis

8.8.1 Planned Genetic Analysis Sample Collection

The planned genetic analysis sample should be drawn for planned analysis of the association between genetic variants in DNA and drug response. This sample will not be collected at the site if there is either a local law or regulation prohibiting collection, or if the IRB/IEC does not approve the collection of the sample for these purposes. If the sample is collected, leftover extracted DNA will be stored for FBR if the participant provides documented informed consent for FBR. If the planned genetic analysis is not approved, but FBR is approved and consent is given, this sample will be collected for the purpose of FBR.

Sample collection, storage, and shipment instructions for planned genetic analysis samples will be in the Operations/Laboratory Manual.

8.9 Future Biomedical Research Sample Collection

If the participant provides documented informed consent for FBR, the following specimens will be obtained as part of FBR:

Leftover DNA for future research

8.10 Health Economics Medical Resource Utilization and Health Economics

Medical Resource Utilization and Health Economics are not evaluated in this study.

8.11 **Visit Requirements**

Visit requirements are outlined in Section 1.3. Specific procedure-related details are provided in Section 8.

8.11.1 Screening

Approximately 4 weeks before intervention allocation/randomization, potential participants will be evaluated to determine that they fulfill the entry requirements as set forth in Section 5.

Participants may be rescreened after consultation with the Sponsor. Rescreening should include all screening procedures listed in the SoA, including consent review, Rescreen procedures cannot be conducted the day prior to intervention allocation/randomization if there are Day -1 procedures planned per protocol.

Treatment Period Visit 8.11.2

Refer to the SoA (Section 1.3) and Administrative and General Procedures (Section 8.1).

8.11.3 Participants Discontinued From Study Intervention but Continuing to be Monitored in the Study

At any point if a participant discontinues from treatment but continues to be monitored in the study, all study procedures specified in the SoA may be completed at the discretion of the investigator and with Sponsor agreement. The subset of study procedures completed will be communicated in a PCL.

8.11.4 **Poststudy**

08CYXG

Participants will be required to return to clinic approximately 28 days after the last dose of study intervention for the poststudy visit. If the poststudy visit occurs less than 28 days after the last dose of study intervention, a subsequent follow-up telephone call should be made at 28 days post the last dose of study intervention to determine if any AEs have occurred since the poststudy clinic visit.

8.11.5 Critical Procedures Based on Study Objectives: Timing of Procedure

For this study, the VL and PBMC blood sample for MK-8527 are the critical procedures.

At any postdose time point, the PBMC blood sample for MK-8527 needs to be collected as close to the exact time point as possible. All other procedures should be completed as close to the prescribed/scheduled time as possible. Study procedures can be performed prior or after the prescribed/scheduled time.

The order of priority can be changed during the study with joint agreement of the investigator and the Sponsor Clinical Director.

Any nonscheduled procedures required for urgent evaluation of safety concerns take precedence over all routine scheduled procedures.

The following variance in procedure collection times will be permitted.

• PK Collection (MK-8527 plasma and MK-8527-TP PBMC) and pharmacodynamic collection (viral load) as outlined in [Table 5].

PK Collection	PK Collection Window
0 to <1 h	5 min
1 to <2 h	10 min
2 to <24 h	15 min
24 to <48 h	1 h
48 to <96 h	2 h
96 to 168 h	4 h
>168 to <672 h	24 h
672 h	48 h

Table 5 Pharmacokinetic (Blood) Collection Windows

- Predose standard safety evaluations: VS and ECG up to 3 hours; laboratory safety tests and physical exam up to 24 hours
- Postdose standard safety evaluations: VS, ECG, laboratory safety tests, and physical exam
 - <24 hours postdose may be obtained within 15 min of the theoretical sampling time
 - 24 hours to <48 hours postdose may be obtained within 1 hour of the theoretical sampling time
 - 48 hours to <96 hours postdose may be obtained within 2 hours of the theoretical sampling time
 - 96 hours to 168 hours postdose may be obtained within 4 hours of the theoretical sampling time
 - >168 hours to <672 hours postdose may be obtained within 24 hours of the theoretical sampling time
 - 672-hours postdose may be obtained within 48 hours of the theoretical sampling time

8.11.6 Study Design/Dosing/Procedures Modifications Permitted Within Protocol Parameters

This is a Phase 1 assessment of MK-8527 in humans, and the PK, pharmacodynamic, and safety profiles of the compound are still being elucidated. This protocol is written with some flexibility to accommodate the inherent dynamic nature of Phase 1 clinical studies. Modifications to the dose, dosing regimen, and/or clinical or laboratory procedures currently outlined may be required to achieve the scientific goals of the study objectives and/or to ensure appropriate safety monitoring of the study participant

PROTOCOL/AMENDMENT NO.: 004-02

As such, some alterations from the currently outlined dose and/or dosing regimen may be permitted based on newly available data, but the maximum daily dose may not exceed those currently outlined in the protocol.

- Entire panel(s) may be omitted
- Adjustment of the dosing interval (eg, divided doses [bid to qd, qd to bid, tid, or vice versa])
- Instructions to take study intervention with or without food or drink may also be modified based on newly available data
- Modification of the PK/pharmacodynamic sample processing and shipping details based on newly available data

The PK/pharmacodynamic sampling scheme currently outlined in the protocol may be modified during the study based on newly available PK or pharmacodynamic data (eg, to obtain data closer to the time of peak plasma concentrations). If indicated, these collected samples may also be assayed in an exploratory manner for metabolites and/or additional pharmacodynamic markers.

Up to additional 50 mL of blood may be drawn for safety, PK, and/or pharmacodynamic analyses. The total blood volume withdrawn from any single participant will not exceed the maximum allowable volume during his/her participation in the entire study (Appendix 8).

The timing of procedures for assessment of safety procedures (eg, vital signs, ECG, safety laboratory tests, etc) may be modified during the study based on newly available data. Additional laboratory safety tests may be added to blood samples previously drawn to obtain additional safety information. These changes will not increase the number of study procedures for a given participant during his/her participation in the entire study.

It is understood that the current study may use some or none of the alterations described above. Any alteration made to this protocol to meet the study objectives must be detailed by the Sponsor in a letter to the Study File and forwarded to the investigator for retention. The letter may be forwarded to the IRB/IEC at the discretion of the investigator.

PROTOCOL/AMENDMENT NO.: 004-02

9 STATISTICAL ANALYSIS PLAN

9.1 Statistical Analysis Plan Summary

This section contains a brief summary of the statistical analyses for this trial. Full detail is in the Statistical Analysis Plan (Sections 9.2-9.9).

Statistical Methods

Primary Objective (Pharmacodynamics): The log10 plasma HIV-RNA (copies/mL) measurements from participants in all panels will be pooled and analyzed based on a longitudinal data analysis model containing fixed effects for dose level, time (predose, 168 hours postdose) and dose level by time interaction, and a random effect for participant. The change from baseline for each dose level at 168 hours post-baseline will be estimated from this model. A posterior distribution for the true mean change from baseline at 168 hours will be generated for each dose level using flat priors under a normal likelihood assumption. Using the posterior distributions for each dose level the posterior distribution of the true mean will be generated, and the posterior probability that the true mean in the log10 plasma HIV-1 RNA reduction from baseline of MK-8527 is at least 1.0 log10 copies/mL will be calculated. A \geq 70% posterior probability for at least one dose level that also exhibits an acceptable safety and tolerability profile will satisfy the primary pharmacodynamics hypothesis.

Primary Objective (Safety): Incidence of AEs will be descriptively summarized. Summary statistics and plots will be generated for the change from baseline values in the VS, ECG parameter values, and selected laboratory safety parameter values for participants, as deemed clinically appropriate. Depending on the safety parameter, the difference from baseline will either be computed on the original scale (raw change from baseline) or on the log scale and back-transformed for reporting (percent change from baseline). Summary statistics for the raw laboratory safety tests, ECGs, and/or VS may also be computed, as deemed clinically appropriate.

9.2 Responsibility for Analyses

The statistical analysis of the data obtained from this study will be conducted by, or under the direct auspices of, the Early Clinical Development Statistics Department in collaboration with the Quantitative Pharmacology and Pharmacodynamic Department and Translational Medicine Department of the Sponsor.

If, after the study has begun, changes are made to the statistical analysis plan stated below, then these deviations to the plan will be listed, along with an explanation as to why they occurred, in the Clinical Study Report.

9.3 Hypothesis/Estimation

Primary

At a dose that is safe and generally well tolerated, MK-8527 has antiretroviral activity, as measured by change from predose in plasma HIV-1 RNA (log10 copies/mL) at 168 hours postdose. That is, the true mean difference in the plasma HIV-1 RNA reduction from predose between MK-8527 is at least 1.0 log10 copies/mL.

Secondary

The GM C168h MK-8527-TP will be estimated.

9.4 Analysis Endpoints

Primary Pharmacodynamic Endpoint

The primary pharmacodynamic variables in this study include plasma HIV -1 RNA reduction from predose at 4, 24, 96, 120, 144, 168, 240, 336, 504 and 672 hours postdose. The change in VL from predose to 168 hours is of primary interest.

Primary Safety Endpoint

The primary safety endpoints in this study include all types of AEs, in addition to laboratory safety assessments, ECGs, and VS.

Secondary Endpoints

The secondary endpoints in this study include AUC0-168hr, T_{max} , C_{max} , C168hr, AUC0-last, AUC0-inf, apparent terminal t1/2 for MK-8527-TP in PBMC and AUC0-last, AUC0-inf, T_{max} , C_{max} , Clast, and apparent terminal t1/2 for plasma MK-8527 following single oral administration of MK-8527 on Day 1.

9.5 Analysis Populations

The following populations are defined for the analysis and reporting of data. All participants will be reported, and their data analyzed, according to the treatment(s) they actually received.

All Participants as Treated (APaT) – The population includes all participants who received at least one dose of the investigational drug. This population will be used for assessments of safety and tolerability.

Per-Protocol (PP) – The population includes the subset of participants who comply with the protocol sufficiently to ensure that generated data will be likely to exhibit the effects of treatment, according to the underlying scientific model. Compliance covers such considerations as exposure to treatment, availability of measurements and absence of major protocol deviations. Major protocol deviations will be identified to the extent possible by individuals responsible for data collection/compliance, and its analysis and interpretation.

PROTOCOL/AMENDMENT NO.: 004-02

Any participants or data values excluded from analysis will be identified, along with their reason for exclusion, in the CSR. At the end of the study, all participants who are compliant with the study procedure as aforementioned and have available data from at least one treatment will be included in the primary analysis dataset. This population will be used for the primary pharmacodynamic, secondary PK and exploratory PK and pharmacodynamic analyses.

9.6 Statistical Methods

Primary (Pharmacodynamics)

The log10 plasma HIV-RNA (copies/mL) measurements from participants in all panels will be pooled and analyzed based on a longitudinal data analysis (LDA) model containing fixed effects for dose level, time (predose, 168 hours postdose) and dose level by time interaction, and a random effect for participant. The response vector consists of the baseline and 168 hours post-baseline values. Time is treated as a categorical variable so that no restriction is imposed on the trajectory of means over time. The change from baseline for each dose level at 168 hours post-baseline will be estimated from this model. A posterior distribution for the true mean change from baseline at 168 hours will be generated for each dose level using flat priors under a normal likelihood assumption.

Using the posterior distributions for each dose level the posterior distribution of the true mean will be generated, and the posterior probability that the true mean in the log10 plasma HIV-1 RNA reduction from baseline of MK-8527 is at least 1.0 log10 copies/mL will be calculated.

A 70% posterior probability for at least one dose level that also exhibits an acceptable safety and tolerability profile will satisfy the primary pharmacodynamics hypothesis. To address the exploratory objective related to antiretroviral activity at 672 hours post-baseline, a similar analysis will be performed using VL measurements at baseline and 672 hours post-baseline. Similar exploratory analyses may be performed at timepoints earlier than 168 hours postbaseline.

Primary (Safety)

Incidence of AEs will be descriptively summarized. Summary statistics and plots will be generated for the change from baseline values in the VS, ECG parameter values, and selected laboratory safety parameter values for participants, as deemed clinically appropriate. Depending on the safety parameter, the difference from baseline will either be computed on the original scale (raw change from baseline) or on the log scale and back-transformed for reporting (percent change from baseline). Summary statistics for the raw laboratory safety tests, ECGs, and/or VS may also be computed, as deemed clinically appropriate.

Secondary (Pharmacokinetic)

Values of MK-8527 plasma and intracellular MK-8527-TP in PBMC pharmacokinetic parameters AUC0-168, AUC0-last, AUC0-inf, C_{max}, and C168hr from participants in all panels will be analyzed. Each PK parameter will be analyzed separately for plasma and

MK-8527-004-02 FINAL PROTOCOL 19-JUL-2023 Confidential

DUCT: MK-8527 70

PBMC. The PK log transformed and analyzed based on a linear model containing a fixed effect for dose level. The 95% confidence intervals for the means will be constructed on the natural log scale and will reference the t-distribution. Exponentiating the means will yield estimates for the population geometric means on the original scale. Data will be examined for departures from the assumptions of the statistical model(s) as appropriate; eg, heteroscedasticity, nonnormality of the error terms. Distribution-free methods may be used if a serious departure from the assumptions of the model(s) is observed, or suitable data transformation may be applied.

Individual values will be listed for each MK-8527 plasma and intracellular MK-8527-TP in PBMC PK parameter (AUC0-168, AUC0-last, AUC0-inf, T_{max}, C_{max}, C168hr, and apparent terminal t1/2.) by dose level, and the following (non-model-based) descriptive statistics will be provided: N (number of participants with non-missing data), arithmetic mean, standard deviation, arithmetic percent CV (calculated as 100 x standard deviation/arithmetic mean), median, minimum, maximum, geometric mean, and geometric percent CV (calculated as 100 x sqrt(exp(s2) -1), where s2 is the observed variance on the natural log-scale).

Secondary and Exploratory (Pharmacokinetic/Pharmacodynamic)

The PK-pharmacodynamic and dose-pharmacodynamic association of MK-8527 will be explored. Graphs to visualize the association of the reduction in log10 plasma HIV-1 RNA levels with various plasma and intracellular MK-8527-TP in PBMC parameters (eg, C168hr, C336hr, C672hr, AUC0-168hr, AUC0-last, AUC0-inf, and C_{max}) and dose may be generated. Exploratory linear and/or non-linear model fits may be considered, as appropriate. Exposure levels and doses that result in various proportions of the population (eg, 80%, 90%) that have at least 1.0 log10 reduction from baseline in plasma HIV-1 RNA levels with high confidence may be estimated.

The duration of antiretroviral suppression after a single dose of MK-8527 will be evaluated with individual plots across time.

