2 INTRODUCTION

2.1 Study Rationale

The purpose of this study is to assess the activity of single doses of MK-8527 in ART-naïve HIV-1 infected participants for a planned once weekly dosing regimen. A previous single dose trial of MK-8527 in HIV infected participants (MK-8527-002) established robust efficacy of 3 mg and 10 mg doses. However, while a single 1 mg dose was highly efficacious in three of five participants, two participants did not achieve the efficacy target, possibly due to confounding factors. This study is being performed to more definitively establish the lowest efficacious dose of MK-8527 as monotherapy, therefore guiding dose selection for future studies.

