Three Phase 1 studies of MK-8527 have been completed. MK-8527-001 was a randomized, placebo controlled, alternating panel, double-blind trial evaluating the safety, tolerability, and PK of single oral doses of MK-8527 in healthy adult participants.

MK-8527-004-02 FINAL PROTOCOL Confidential

08CYXG

As detailed in the IB, PK of plasma MK-8527 in P001 was dose proportional over the entire single dose range.

There was no clinically meaningful effect of a high-fat meal on MK-8527 PK.

MK-8527-003 was a randomized, placebo-controlled, serial panel, multiple rising dose double-blinded study evaluating safety, tolerability and PK of multiple doses of MK-8527 in healthy participants.

MK-8527-002 was an open-label, single dose, multiple panel study to evaluate the safety, tolerability, antiretroviral activity, and PK of MK-8527 monotherapy in treatment naïve HIV 1 infected participants. Participants received a single oral dose of 1 mg, 3 mg, or 10 mg of MK-8527. All doses were generally well-tolerated, with no SAEs, ECIs, or discontinuations due to an AE. Only 2 participants reported a total of 3 AEs (pharyngitis, dizziness, insomnia), and the AEs were considered unrelated to study intervention. There were no abnormalities in laboratory values, vital signs, or ECGs. PK of both parent and MK-8527-TP was generally similar between HIV+-positive participants in P002 and in non-HIV-infected study participants in P001.

Single doses of 3 mg and 10 mg were shown to achieve target intracellular MK-8527-TP C168hr of 0.2 pmol/ 10^6 cells. Single 1 mg doses led to robust declines in viral load in 3 of the 5 participants but failed to achieve target reduction in 2 of the 5 participants, 1 of whom had no response. Across all 3 Phase 1 studies, MK-8527 was rapidly absorbed with a median T_{max} of 0.5 to 1 hour. Plasma concentrations decreased in a biphasic manner with an apparent terminal half-life of \sim 36 to 81 hours and exposures appeared to increase in an approximately dose-proportional manner. The active MK-8527-TP moiety reached intracellular C_{max} at a median T_{max} of 10 to 48 hours and the concentrations in PBMC declined with an apparent terminal half-life of \sim 94 to 291 hours across doses.

Refer to the IB for additional information on these Phase 1 studies.

08CYXG

MK-8527-004-02 FINAL PROTOCOL

19-JUL-2023

Confidential

[figure not shown]

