3 HYPOTHESES, OBJECTIVES, AND ENDPOINTS

Hypotheses are aligned with objectives in the Objectives and Endpoints table.

Study Population: Treatment naïve HIV-1 infected participants

Primary Objective	Primary Endpoint
- To evaluate the antiretroviral activity of MK-8527 in HIV-1 infected participants. - Hypothesis: At a dose that is safe and generally well tolerated, MK-8527 has antiretroviral activity, as measured by change from predose in plasma HIV-1 RNA (log10 copies/mL) at 168 hours postdose. That is, the true mean difference in the plasma HIV-1 RNA reduction from predose after MK-8527 is at least 1.0 log10 copies/mL.	- Plasma HIV-RNA (log10 copies/mL) reduction from predose
- To evaluate the safety and tolerability of MK-8527 in HIV-1 infected participants.	- Adverse events
Secondary Objectives	Secondary Endpoints
 To evaluate the intracellular PK of MK-8527-TP in PBMC after administration of single oral doses of MK-8527 to HIV-1 infected participants. Estimation: The GM C168h MK-8527-TP will be estimated 	- MK-8527-TP AUC0-168, AUC0-last, AUC0-inf, T _{max} , C _{max} , C168hr, and apparent terminal t1/2 in PBMC.
- To evaluate plasma PK of MK-8527 after administration of single oral doses to HIV-1 infected participants.	- MK-8527 plasma AUC0-last, AUC0-inf, $T_{\text{max}},C_{\text{max}},Clast,$ and apparent terminal $t1/2$
- To evaluate the PK- pharmacodynamic association of intracellular MK-8527-TP with viral load reduction.	- PK (MK-8527-TP in PBMC) / pharmacodynamic (plasma HIV-1 RNA) correlation.

PRODUCT: MK-8527 PROTOCOL/AMENDMENT NO.: 004-02

Tertiary/Exploratory Objectives	Tertiary/Exploratory Endpoints
- To evaluate the relationship between dose and antiretroviral activity of MK-8527.	- Dose-response (plasma HIV-1 RNA) relationship.
- To explore the relationship between genetic variation at response to the treatment administration and mechanisms of disease. Variation across the human genome may be analyzed for association with the clinical data collected in this study.	- Germline genetic variation and association to clinical data collected in this study

08CYXG

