4.2 Scientific Rationale for Study Design

This protocol is designed with up to 4 panels and will primarily assess the short-term antiretroviral activity of MK-8527 monotherapy in ART-naïve HIV-1 infected participants. Data from this study will aid dose selection in future studies. The goals of this study will be achieved by enrolling a minimum number of participants using the shortest treatment duration possible. This design provides the advantages of progressing through multiple dose levels expeditiously while allowing sufficient time intervals to assess durability of effect in each panel. The time intervals between dosing allows for careful review of emerging data to permit a decision on advancing to the next panel at an appropriate dose to fully explore the dose-response profile of the compound.

The doses to be tested in this study are designed based on findings in the previous MK-8527 002 study, where 3 mg and 10 mg doses were highly efficacious, but 1 mg doses failed to achieve target reductions in viral load in 2 of the 5 participants. Preliminary results from Panels A and B of this study demonstrated antiviral efficacy at both the 1.0 mg and 0.5 mg doses of MK-8527. This study will evaluate the efficacy and kinetics by which MK-8527 reduces HIV-1 RNA VL over time and establish the lowest efficacious monotherapy dose in suppressing viral replication.

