4.4.1 Clinical Criteria for Early Study Termination

There are no prespecified criteria for terminating the study early.

A primary objective of this Phase 1 study is to identify the lowest dose of MK-8527 that is well tolerated, has acceptable PK, pharmacodynamic, and achieves target viral load reduction. Therefore, it is possible that Panel D may not be enrolled if this objective is achieved after review of data from Panels A through C. This would not be defined as early termination of the study, but rather an earlier than anticipated achievement of the study objective(s). If a finding (eg, PK, pharmacodynamic, efficacy, biologic targets, etc.) from another preclinical or clinical study using the study intervention(s), comparator(s), drug(s) of the same class, or methodology(ies) used in this study results in the study(s) or program being stopped for non-safety reasons, this also does not meet the definition of early study termination.

Early study termination is defined as a permanent discontinuation of the study due to unanticipated concerns of safety to the study participants arising from clinical or preclinical studies with the study intervention(s), comparator(s), drug(s) of the same class, or methodology(ies) used in this study.

35

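### Does the plan need a written rule for naming the lowest efficacious dose?

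*Combined protocol and SAP*

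**What the plan says.** Section 3 gives two primary objectives. One is efficacy, "To evaluate the antiretroviral activity of MK-8527 in HIV-1 infected participants"; the other is safety and tolerability. The relation between dose and activity is listed as exploratory. Section 9.3 words the hypothesis for a single suitable dose: "At a dose that is safe and generally well tolerated, MK-8527 has antiretroviral activity". Section 9.6 follows with the any-dose rule: "A 70% posterior probability for at least one dose level that also exhibits an acceptable safety and tolerability profile will satisfy the primary pharmacodynamics hypothesis". The model in 9.6 has a dose-by-time term and generates a posterior for the mean change at 168 hours at each dose level. Panels C and D share the 0.25 mg dose and so form one level.

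Section 4.4.1 uses other language. It counts among the primary aims to "identify the lowest dose of MK-8527 that is well tolerated, has acceptable PK, pharmacodynamic, and achieves target viral load reduction", and adds that "it is possible that Panel D may not be enrolled if this objective is achieved after review of data from Panels A through C".

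The background describes the earlier study by participant. Section 2.1 says that "while a single 1 mg dose was highly efficacious in three of five participants, two participants did not achieve the efficacy target", and Section 4.2 repeats that "1 mg doses failed to achieve target reductions in viral load in 2 of the 5 participants". The exploratory part of Section 9.6 allows, but does not require, estimation of doses at which, for example, 80% or 90% of the population reach a 1.0 log10 reduction.

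**The concern.** Sections 2.1, 2.2.3 and 4.2 all give the lowest efficacious dose as the reason for the study. The only decision rule in Section 9 is met once any dose passes. Section 2.2.3 already reports mean reductions above 1.0 log10 at 1.0 mg and 0.5 mg, so the hypothesis may be satisfied whatever 0.25 mg does. The question left for Panels C and D then seems to have no written criterion.

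There also appear to be two standards. Section 9.6 judges the mean, whereas the background calls 1 mg unsettled because 2 of 5 individuals missed the target. If these disagreed at 0.25 mg, the choice between them could be made after the data were seen, and it would carry into dose selection for later studies.

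**Working it through.** **Inputs.** Target 1.0 log10 and 70% posterior probability (Sections 4.2.1.3 and 9.6); SD 0.3 with mean 1.25, SD 0.43 with mean 1.3, and n = 6 (Section 9.9); n = 12 if Panels C and D are both enrolled. Reductions are taken as normal with known SD, and z(0.70) = 0.5244. Paired figures below are for SD 0.3 / 0.43.

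**1. The plan's own figure.** With a flat prior a dose passes when its observed mean is at least 1 + 0.5244 × SD/√n. Power is Φ((μ − 1)/(SD/√n) − 0.5244).
- SD 0.3, μ 1.25: Φ(0.25/0.1225 − 0.5244) = Φ(1.517) = 93.5%.
- SD 0.43, μ 1.3: Φ(0.30/0.1755 − 0.5244) = Φ(1.184) = 88.2%.

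Section 9.9 states about 80%, so it is conservative for these inputs. That is a separate matter, and nothing below uses the 80%.

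**2. How far the mean and the share can part.** At n = 6 a dose just passes at 1 + 0.5244 × 0.1225 = 1.064, or 1 + 0.5244 × 0.1755 = 1.092. If that were the true mean, the share of participants reaching 1.0 would be Φ(0.5244/√6) = 58.5%. At n = 12 it is Φ(0.5244/√12) = 56.0%. The SD cancels: this is a property of any mean rule at its boundary, not a peculiarity of this plan.

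At the planning means the expected share is Φ(0.25/0.3) = 79.8% and Φ(0.30/0.43) = 75.7%. Both are already below 80%, so observed shares below 80% will be common. With six participants, two or more miss 1.0 in 35% / 45% of trials. A simulation (400,000 trials, residual variance pooled across doses) puts the figure at 31% / 38% among trials where the dose passes. Part of this is discreteness: 5 of 6 clears 80% and 4 of 6 does not.

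**3. Would the planned output show 0.25 mg failing?** Assume a true mean of 0.9 at 0.25 mg and n = 6. The chance that 0.25 mg passes its own 70% is Φ(−0.1/0.1225 − 0.5244) = 9.0%, or Φ(−0.1/0.1755 − 0.5244) = 13.7%. It therefore falls short in 91.0% / 86.3% of trials. With the two higher doses at the planning means, the any-dose rule passes while 0.25 mg fails in 91% / 86% of simulated trials. In each of these the Section 9.6 posterior for 0.25 mg is below 70% and is part of the planned analysis.

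**4. Is there really a second standard?** Section 2.2.2 says one of the two participants who missed the target at 1 mg had no response. Assume that participant scored 0 and the other scored at most 1.0. With n = 5 the mean rule needs 1 + 0.5244 × 0.3/√5 = 1.07, or 1 + 0.5244 × 0.43/√5 = 1.10. The three responders would have to average at least (5 × 1.070 − 1.0)/3 = 1.45, or (5 × 1.101 − 1.0)/3 = 1.50. The individual values are not given, so 1 mg may have been unsettled on the mean as well. The account of that study does not show that a responder share was the criterion.

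**5. The passages side by side.** Section 4.4.1 speaks of a dose reaching the target reduction. Section 4.2.1.3 defines that target through the 70% posterior probability and says the level was chosen so that doses able to meet it go into later studies. Section 9.6 computes it by dose level, and Section 2.2.3 judges Panels A and B by the mean. Taken together, the lowest efficacious dose is the lowest level at or above 70% with acceptable safety.

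**The case for a change.** The strongest point for a change is that no sentence makes this link. Section 4.4.1 calls the aim primary, Section 3 does not, and the clause on Panel D depends on that aim being achieved. Section 4.4.1 also asks for acceptable PK without a criterion. Writing the rule before the 0.25 mg data are read would cost only wording.

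The mismatch between 4.4.1 and Section 3 stands. The rest carries less weight:
- **Panel D.** Section 6.6 leaves it to a joint decision of investigator and sponsor once Panel C viral load data are available. Section 8.11.6 allows whole panels to be omitted, and 4.4.1 itself speaks only of a possibility. That discretion is usual in Phase 1.
- **PK.** Section 2.2.2 gives a target intracellular concentration at 168 hours of 0.2 pmol/10^6 cells, and Section 9.3 plans to estimate the geometric mean at that time. Sections 4.3.1 and 4.3.2 are not shown, so the absence of a PK criterion cannot be inferred.
- **Responder share.** The 80% and 90% figures are optional examples in an exploratory analysis. With 6 to 12 participants per dose, an observed share is too imprecise to decide on.
- **A naming sentence.** It would write down the reading the documents already support. It would still rest on the word acceptable for PK, so it would not remove the judgement.

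**Conclusion.** No change follows. Calling the lowest-dose aim primary in Section 4.4.1 is a clerical slip against Section 3, and the missing naming rule is a gap that any analyst would fill the same way from Sections 4.2.1.3 and 9.6. The any-dose rule is right for the hypothesis it serves, and it does not hide a failing dose: at an assumed true mean of 0.9, the 0.25 mg posterior would miss 70% in about 91% (SD 0.3) or 86% (SD 0.43) of trials with six participants. The mean and the responder share can part near the boundary (58.5% expected at n = 6, 56.0% at n = 12), but that holds for any rule on a mean, and the plan does not make the share a criterion. The figures rest on normal data and the Section 9.9 SDs. The conclusion also rests on each dose level's posterior being reported, which Section 9.6 calls for by generating one per level. Added wording would change no model, estimate, sample size or decision-maker.
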